## Regulatory Considerations

This study will be conducted in accordance with:

- consensus ethics principles derived from international ethics guidelines, including the Declaration of Helsinki and Council for International Organizations of Medical Sciences International Ethical Guidelines
- 2) applicable ICH GCP Guidelines
- 3) applicable laws and regulations

Some of the obligations of the sponsor will be assigned to a third party organization.

## **Protocol Signatures**

The sponsor's responsible medical officer will approve the protocol, confirming that, to the best of his or her knowledge, the protocol accurately describes the planned design and conduct of the study.

After reading the protocol, each principal investigator will sign the protocol signature page and send a copy of the signed page to a Lilly representative.

## Final Report Signature

The investigator or designee will sign the clinical study report for this study, indicating agreement with the analyses, results, and conclusions of the report.

The sponsor's responsible medical officer and statistician will sign/approve the final clinical study report for this study, confirming that, to the best of his or her knowledge, the report accurately describes the conduct and results of the study.

## **Data Quality Assurance**

To ensure accurate, complete, and reliable data, Lilly or its representatives will do the following:

- provide instructional material to the study sites, as appropriate.
- provide training to instruct the investigators and study coordinators. This training will give instruction on the protocol, the completion of the eCRFs, and study procedures.
- make periodic visits to the study site.
- be available for consultation and stay in contact with the study site personnel by mail, telephone, and/or fax.
- review and evaluate eCRF data and/or use standard computer edits to detect errors in data collection.
- conduct a quality review of the database.

In addition, Lilly or its representatives will periodically check a sample of the subject data recorded against source documents at the study site. The study may be audited by Lilly and/or regulatory agencies at any time. Investigators will be given notice before an audit occurs.

The investigator will keep records of all original source data. This might include laboratory tests, medical records, and clinical notes. If requested, the investigator will provide the sponsor, applicable regulatory agencies, and applicable ERBs with direct access to the original source documents.

#### Data Collection Tools/Source Data

An electronic data capture system will be used in this study. The site must define and retain all source records and must maintain a record of any data where source data are directly entered into the data capture system.

## Study and Site Closure

## **Discontinuation of Study Sites**

Study site participation may be discontinued if Lilly or its designee, the investigator, or the ERB of the study site judges it necessary for medical, safety, regulatory, or other reasons consistent with applicable laws, regulations, and GCP.

## Discontinuation of the Study

The study will be discontinued if Lilly or its designee judges it necessary for medical, safety, regulatory, or other reasons consistent with applicable laws, regulations, and GCP.

## Appendix 4. Hepatic Monitoring Tests for Treatment-Emergent Abnormality

Selected tests may be obtained in the event of a treatment-emergent hepatic abnormality and may be required in follow-up with patients in consultation with Lilly or its designee CRP.

Hepatic Monitoring Tests	Hepatic	Mon	itoring	Tests
---------------------------------	---------	-----	---------	-------

Hepatic Hematologya	Haptoglobin a	
Hemoglobin		
Hematocrit	Hepatic Coagulationa	
RBC	Prothrombin time	
WBC	Prothrombin time, INR	
Neutrophils		
Lymphocytes	Hepatic Serologies a,b	
Monocytes	Hepatitis A antibody, total	
Eosinophils	Hepatitis A antibody, IgM	
Basophils	Hepatitis B surface antigen	
Platelets	telets Hepatitis B surface antibody	
	Hepatitis B core antibody	
Hepatic Chemistrya	Hepatitis C antibody	
Total bilirubin	Hepatitis E antibody, IgG	
Conjugated bilirubin	Hepatitis E antibody, IgM	
Alkaline phosphatase		
ALT	Anti-nuclear antibody a	
AST	Alkaline Phosphatase Isoenzymesa	
GGT	Anti-smooth muscle antibody (or anti-actin	
CPK	antibody) a	

Abbreviations: ALT = alanine aminotransferase; AST = aspartate aminotransferase; CPK = creatinine phosphokinase; GGT = gamma-glutamyl transferase; Ig = immunoglobulin; INR = international normalized ratio; RBC = red blood cell; WBC = white blood cell.

- a Assayed by Lilly-designated or local laboratory.
- b Reflex/confirmation dependent on regulatory requirements and/or testing availability.

## Appendix 5. Blood Sampling Summary

This table summarizes the approximate number of venipunctures and blood volumes for all blood sampling (screening, safety laboratories, and bioanalytical assays) during the study. Fewer venipunctures and blood draws may actually occur, but this will not require a protocol amendment.

**Protocol I8D-MC-AZEP Sampling Summary** 

Purpose	Maximum Blood Volume per Sample (mL)	Maximum Number of Blood Samples	Maximum Total Volume (mL)
Screening tests a	11	1	11
Clinical laboratory testsa	7.5	3	22.5
Pharmacokinetics b	4	19	76
Pharmacogenetics	10	1	10
Total			119.5
Total for clinical purposes rounded up to nearest 10 mL			120

a Additional samples may be drawn if needed for safety purposes.

b Including the 3 additional pharmacokinetic samples, if needed.

# Appendix 6. Protocol Amendment I8D-MC-AZEP(d) Summary An Absolute Bioavailability Study of LY3314814 in Healthy Subjects Using an Intravenous Tracer Method

Protocol I8D-MC-AZEP, An Absolute Bioavailability Study of LY3314814 in Healthy Subjects Using an Intravenous Tracer Method, has been amended. The new protocol is indicated by Amendment (d) and will be used to conduct the study in place of any preceding version of the protocol.

The protocol now states that

If the investigator identifies a subject who did not meet enrollment criteria and was inadvertently enrolled prior to any dosing, the subject will be discontinued from the study with no further data collection or study procedures performed. If the investigator identifies a subject who did not meet enrollment criteria and was inadvertently enrolled and dosed, the subject will be discontinued from the study and early discontinuation procedures performed (Section 8.1.1.).

#### **Revised Protocol Sections**

Note:	All deletions have been identified by strikethroughs.
	All additions have been identified by the use of underscore.

## 8.1.1. Discontinuation of Inadvertently Enrolled Subjects

If the sponsor or investigator identifies a subject who did not meet enrollment criteria and was inadvertently enrolled, a discussion must occur between the Lilly CP or CRP and the investigator to determine if the subject may continue in the study. If both agree it is medically appropriate to continue, the investigator must obtain documented approval from the Lilly CP or CRP to allow the inadvertently enrolled subject to continue in the study with or without continued treatment with investigational product.

If the investigator identifies a subject who did not meet enrollment criteria and was inadvertently enrolled prior to any dosing, the subject will be discontinued from the study with no further data collection or study procedures performed. If the investigator identifies a subject who did not meet enrollment criteria and was inadvertently enrolled and dosed, the subject will be discontinued from the study and early discontinuation procedures performed.

10. INTERIM ANALYSES		
11. CHANGES FROM THE PROTOCOL SPE		
12. REFERENCES		
13. DATA PRESENTATION		
13.1 Derived Parameters		
13.2 Missing Data		
13.3 Insufficient Data for Presentation		

2. ABBREVIATIONS

Abbreviations pertain to the Statistical Analysis Plan (SAP) only (not the tables, figures and listings [TFLs]).

%AUC(t_{last}-∞) Percentage of AUC(0-∞) extrapolated

AE Adverse event

ANOVA Analysis of variance

AUC Area under the concentration versus time curve

AUC(0-∞) Area under the concentration versus time curve from time zero to

infinity

AUC(0- t_{last}) Area under the concentration versus time curve from time zero to

time t, where t is the last time point with a measurable concentration

BQL Below the lower limit of quantitation

CL Total body clearance of drug calculated after IV administration

C_{last} Last quantifiable drug concentration

CL/F Apparent total body clearance of drug calculated after extra vascular

administration

C_{max} Maximum observed drug concentration

CRF Case Report Form

CRU Clinical Research Unit
CSR Clinical Study Report
CV Coefficient of variation

DN Dose normalised EC Early Clinical

ECG Electrocardiogram

e.g. For example (Latin: exempli gratia)

ICH International Council on Harmonisation

IV Intravenous

LLOQ Lower limit of quantification

MedDRA Medical Dictionary for Regulatory Activities

PK Pharmacokinetic

SAP Statistical Analysis Plan

SD Standard deviation

Final, 05 Jan 2018 Page 3 of 14

TFLs	Tables, Figures, and Listings	
t _{1/2}	Half-life associated with the terminal rate constant (λ_z) in non-compartmental analysis	
t_{max}	Time of maximum observed drug concentration	
WHO	World Health Organization	
V_{ss}	Volume of distribution at steady state after IV administration	
V_{ss}/F	Apparent volume of distribution at steady state after extra-vascular administration	
V_z	Volume of distribution during the terminal phase after IV administration	
V _z /F	Apparent volume of distribution during the terminal phase after extra-vascular administration	

Final, 05 Jan 2018 Page 4 of 14

3. INTRODUCTION

This SAP has been developed after review of the Clinical Study Protocol (final version dated 07 November 2016), Protocol Amendment (a) (final version dated 07 June 2017), Protocol Amendment (b) (final version dated 21 August 2017), Protocol Amendment (c) (final version dated 06 September 2017), and Protocol Amendment (d) (final version dated 13 October 2017).

This SAP describes the planned analysis of the safety, tolerability and pharmacokinetic (PK) data from this study. A detailed description of the planned TFLs to be presented in the clinical study report (CSR) is provided in the accompanying TFL shell document.

The intent of this document is to provide guidance for the statistical and PK analyses of data. In general, the analyses are based on information from the protocol, unless they have been modified by agreement between Eli Lilly and Company and PPD. A limited amount of information concerning this study (e.g., objectives, study design) is given to help the reader's interpretation. This SAP must be signed off prior to first subject administration for this study. When the SAP and TFL shells are agreed upon and finalized, they will serve as the template for this study's CSR.

This SAP supersedes the statistical considerations identified in the protocol; where considerations are substantially different, they will be so identified. If additional analyses are required to supplement the planned analyses described in this SAP, they may be performed and will be identified in the CSR. Any substantial deviations from this SAP will be agreed upon between Eli Lilly and Company and PPD and identified in the CSR. Any minor deviations from the TFLs may not be documented in the CSR.

This SAP is written with consideration of the recommendations outlined in the International Council on Harmonisation (ICH) E9 Guideline entitled Guidance for Industry: Statistical Principles for Clinical Trials¹ and the ICH E3 Guideline entitled Guidance for Industry: Structure and Content of Clinical Study Reports².

4. STUDY OBJECTIVES

4.1 Primary Objective

The primary objective is to estimate the absolute bioavailability of LY3314814 following simultaneous administration of a single oral dose of 50 mg LY3314814 and a 2- hour intravenous (IV) infusion of approximately 100 μ g [13 C₄ 15 N₃]-LY3314814(+)- Camsylate (referred to as [13 C₄ 15 N₃]-LY3314814 from this point forward) in healthy subjects.

4.2 Secondary Objectives

The secondary objectives are:

 To assess the safety of LY3314814 following simultaneous administration of a single oral dose of 50 mg LY3314814 and a 2-hour IV infusion of approximately 100 μg [¹³C₄¹⁵N₃]-LY3314814 in healthy subjects.

Final, 05 Jan 2018 Page 5 of 14

To characterize the PK parameters of LY3314814 and [¹³C₄¹⁵N₃]-LY3314814 following simultaneous administration of a single oral dose of 50 mg LY3314814 and a 2-hour IV infusion of approximately 100 μg [¹³C₄¹⁵N₃]-LY3314814 in healthy subjects.

5. STUDY DESIGN

This is a Phase 1, single-center, open-label, single-period study to estimate the absolute bioavailability of LY3314814 in healthy male and female subjects not of childbearing potential.

Subjects will be admitted to the clinical research unit (CRU) on Day -1 and will remain resident in the CRU for at least 48 hours after the start of infusion, followed by outpatient visits on Days 4, 5 and 6. A follow-up visit will occur at least 7 days postdose. On Day 1, following an overnight fast of at least 8 hours, subjects will receive a single oral dose of 50 mg LY3314814 and at approximately the same time an IV infusion of approximately 100 µg [$^{13}C_4^{15}N_3$]-LY3314814 will be started. The infusion will run for 2 hours. Blood samples will be collected predose and up to 120 hours postdose to measure LY3314814 and [$^{13}C_4^{15}N_3$]-LY3314814 concentrations.

6. TREATMENT

The following label for study treatment will be used in the TFLs: 50 mg LY3314814 oral + $100 \mu g [^{13}C_4^{15}N_3]$ -LY3314814 IV. PK data will summarised separately for each administration.

7. SAMPLE SIZE JUSTIFICATION

Up to 8 subjects may be enrolled and dosed to ensure that at least 6 subjects complete and have evaluable PK data.

This sample size is considered adequate for Phase 1 studies evaluating absolute bioavailability and is not intended to meet any a priori statistical requirement.

8. DEFINITION OF ANALYSIS POPULATIONS

The "Safety" population will consist of all enrolled subjects, whether or not they completed all protocol requirements.

The "Pharmacokinetic" population will consist of all subjects who received at least one dose of study drug and have evaluable PK data. Subjects may be excluded from the PK summary statistics and statistical analysis if a subject has an adverse event (AE) of vomiting that occurs at or before 2 times median of the time of maximum observed drug concentration (t_{max}).

All protocol deviations that occur during the study will be considered for their severity/impact and will be taken into consideration when subjects are assigned to analysis populations.

Final, 05 Jan 2018 Page 6 of 14

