## 8.1.1. Discontinuation of Inadvertently Enrolled Subjects

If the investigator identifies a subject who did not meet enrollment criteria and was inadvertently enrolled prior to any dosing, the subject will be discontinued from the study with no further data collection or study procedures performed. If the investigator identifies a subject who did not meet enrollment criteria and was inadvertently enrolled and dosed, the subject will be discontinued from the study and early discontinuation procedures performed.

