#### 9.2.1. Serious Adverse Events

An SAE is any AE from this study that results in one of the following:

- death
- initial or prolonged inpatient hospitalization
- a life-threatening experience (that is, immediate risk of dying)
- persistent or significant disability/incapacity
- congenital anomaly/birth defect
- events considered significant by the investigator based upon appropriate medical judgment

Study site personnel must alert Lilly, or its designee, of any SAE within 24 hours of investigator awareness of the event via a sponsor-approved method. If alerts are issued via telephone, they are to be immediately followed with official notification on study-specific SAE forms. This 24-hour notification requirement refers to the initial SAE information and all follow-up SAE information.

Although all AEs are recorded in the eCRF after signing informed consent, SAE reporting begins after the subject has signed informed consent and has received investigational product. However, if an SAE occurs after signing informed consent, but prior to receiving investigational product, AND is considered reasonably possibly related to a study procedure then it MUST be reported.

Investigators are not obligated to actively seek AEs or SAEs in subjects once they have discontinued from and/or completed the study (the subject summary eCRF has been completed). However, if the investigator learns of any SAE, including a death, at any time after a subject has been discharged from the study, and he/she considers the event reasonably possibly related to the study treatment or study participation, the investigator must promptly notify Lilly.

Pregnancy (maternal or paternal exposure to investigational product) does not meet the definition of an AE. However, to fulfill regulatory requirements, any pregnancy should be reported following the SAE process to collect data on the outcome for both mother and fetus.

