## 10.3. Statistical Analyses

Statistical analysis of this study will be the responsibility of Eli Lilly and Company or its designee.

Pharmacokinetic analyses will be conducted on the full analysis set. This set includes all data from all subjects receiving the investigational product and who have evaluable data. If a subject has an AE of vomiting that occurs at or before 2 times median  $t_{max}$  after dosing then that subject may be excluded from the PK summary statistics and statistical analysis. Safety analyses will be conducted for all enrolled subjects, whether or not they completed all protocol requirements.

Additional exploratory analyses of the data will be conducted as deemed appropriate. Study results may be pooled with the results of other studies for population PK analysis purposes.

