## Appendix 1. Abbreviations and Definitions

Term	Definition
AD	Alzheimer's disease
AE	adverse event: Any untoward medical occurrence in a patient or clinical investigation subject administered a pharmaceutical product that does not necessarily have a causal relationship with this treatment. An AE can therefore be any unfavorable and unintended sign (including an abnormal laboratory finding), symptom, or disease temporally associated with the use of a medicinal (investigational) product, whether or not related to the medicinal (investigational) product.
AUC	area under the drug concentration-time curve
AUC(0-∞)	area under the drug concentration-time curve from zero to infinity
AUC(0-t last )	area under the drug concentration-time curve from time zero to time $t_{last}$ , where $t_{last}$ is the last time point with a measurable concentration
AV	Atrioventricular
BCRP	breast cancer resistance protein
ВМІ	body mass index
C max	maximum observed drug concentration
complaint	A complaint is any written, electronic, or oral communication that alleges deficiencies related to the identity, quality, purity, durability, reliability, safety or effectiveness, or performance of a drug or drug delivery system.
compliance	Adherence to all the trial-related requirements, good clinical practice (GCP) requirements, and the applicable regulatory requirements.
confirmation	A process used to confirm that laboratory test results meet the quality requirements defined by the laboratory generating the data and that Lilly is confident that results are accurate. Confirmation will either occur immediately after initial testing or will require that samples be held to be retested at some defined time point, depending on the steps required to obtain confirmed results.
СР	clinical pharmacologist
CRP	clinical research physician: Individual responsible for the medical conduct of the study. Responsibilities of the CRP may be performed by a physician, clinical research scientist, global safety physician or other medical officer.
CRU	clinical research unit
СҮР	cytochrome P450

**ECG** Electrocardiogram

eCRF electronic case report form

**enroll** The act of assigning a subject to a treatment. Subjects who are enrolled in the trial are those

who have been assigned to a treatment.

**enter** Subjects entered into a trial are those who sign the informed consent form directly or

through their legally acceptable representatives.

**ERB** ethical review board

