9. STATISTICAL METHODOLOGY

9.1 General

Data listings will be provided for all data that is databased. Summary statistics and statistical analysis will only be presented for data where detailed in this SAP. For continuous data, summary statistics will include the arithmetic mean, arithmetic standard deviation (SD), median, min, max and N; for log-normal data (e.g. the PK parameters: Area under the concentration versus time curve [AUC] and the maximum observed drug concentration [C_{max}] the geometric mean and geometric coefficient of variation [CV%] will also be presented. For categorical data, frequency count and percentages will be presented. Data listings will be provided for all subjects up to the point of withdrawal, with any subjects excluded from the relevant population highlighted. Summary statistics and statistical analyses will generally only be performed for subjects included in the relevant analysis population. For the calculation of summary statistics and statistical analysis, unrounded data will be used.

Mean change from baseline is the mean of all individual subjects' change from baseline values. Each individual change from baseline will be calculated by subtracting the individual subject's baseline value from the value at the timepoint. The individual subject's change from baseline values will be used to calculate the mean change from baseline using a SAS procedure such as Proc Univariate.

Data analysis will be performed using SAS® Version 9.4 or greater.

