9.4 Safety and Tolerability Assessments

9.4.1 Adverse events

Where changes in severity are recorded in the Case Report Form (CRF), each separate severity of the AE will be reported in the listings, only the most severe will be used in the summary tables. A pre-existing condition is defined as an AE that starts before the subject has provided written informed consent and is ongoing at consent. A non-treatment emergent AE is defined as an AE which starts after informed consent but prior to dosing. A treatment-emergent AE is defined as an AE which occurs postdose or which is present prior to dosing and becomes more severe postdose.

All AEs will be listed. Treatment-emergent AEs will be summarized by severity and relationship to the study drug. The frequency (the number of AEs, the number of subjects experiencing an AE and the percentage of subjects experiencing an AE) of treatment-emergent AEs will be summarized by Medical Dictionary for Regulatory Activities (MedDRA) version 20.1 system organ class and preferred term. The summary and frequency AE tables will be presented for all causalities and those considered related to the study drug. Any serious AEs will be tabulated. Onset time of AEs will derived relative to the oral administration.

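### The Safety population has no dosing condition, so any enrolled subject who is never dosed would lower the treatment-emergent AE percentages

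*SAP*

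**What the plan says.** SAP 8 states that the Safety "population will consist of all enrolled subjects, whether or not they completed all protocol requirements". Protocol 10.3 agrees: "Safety analyses will be conducted for all enrolled subjects, whether or not they completed all protocol requirements". Neither asks that a dose was given. The PK population, defined in the same SAP section, does require one.

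Protocol Appendix 1 defines enrolling as "The act of assigning a subject to a treatment". Protocol 8.1.1 then provides for an ineligible subject "inadvertently enrolled prior to any dosing, the subject will be discontinued from the study with no further data collection or study procedures performed".

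For the AE tables, SAP 9.4.1 says: "A treatment-emergent AE is defined as an AE which occurs postdose or which is present prior to dosing and becomes more severe postdose". The frequency tables report, besides the number of AEs, "the number of subjects experiencing an AE and the percentage of subjects experiencing an AE". That section names no denominator. The general rule in SAP 9.1 is: "Summary statistics and statistical analyses will generally only be performed for subjects included in the relevant analysis population". SAP 6 gives the tables a single treatment label that combines the oral and IV products.

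**The concern.** The incidence of TEAEs is a secondary endpoint (Protocol 4), and Protocol 3.2.1 says the compound has not been given intravenously before. The percentage should describe people exposed to the products. As written, someone assigned to treatment but never dosed stays in the Safety population. That person cannot have a TEAE, yet counts in the denominator, under a label naming two products that he or she did not receive. With 6 to 8 dosed subjects, one extra person moves the percentage visibly.

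The case is foreseeable. Amendment (d) introduced the present text of Protocol 8.1.1, and SAP 3 says the SAP was written after review of that amendment. The group was recognised in the protocol but not carried into the population definition. Withdrawal before dosing under Protocol 8.2, by the subject's or the investigator's decision, is a second route to the same result.

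**Working it through.** The plan gives no figure to reproduce: SAP 7 and Protocol 10.1 say that the sample size meets no statistical requirement. The check is therefore a reading of the rules followed by denominator arithmetic.

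**Who is in the set**

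1. The Safety population is everyone enrolled (SAP 8, Protocol 10.3).
2. Enrolled means assigned to treatment (Protocol Appendix 1), and enrolment can precede dosing (Protocol 8.1.1).
3. A TEAE occurs or worsens postdose (SAP 9.4.1), so a never-dosed subject contributes 0 to the numerator.
4. Summaries use the relevant analysis population (SAP 9.1). The only safety population defined is the enrolled set, so that subject contributes 1 to the denominator.

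**Size**

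Let D be the number dosed, U the number enrolled but undosed, and x the number of subjects with a TEAE.

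- Percentage as written: x/(D+U)
- Percentage among those dosed: x/D
- Ratio of the two: D/(D+U), so the relative understatement is U/(D+U)

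The plan aims for at least 6 evaluable subjects and up to 8 enrolled and dosed (SAP 7), so D = 6 to 8 is used. The documents give no value for U; 0, 1 and 2 are assumed.

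| D | U = 0 | U = 1 | U = 2 |
|---|---|---|---|
| 8 | 0% | 1/9 = 11.1% | 2/10 = 20.0% |
| 7 | 0% | 1/8 = 12.5% | 2/9 = 22.2% |
| 6 | 0% | 1/7 = 14.3% | 2/8 = 25.0% |

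If 8 is a ceiling on enrolment and not only on dosing, the cells with D+U above 8 drop out. That leaves 12.5% and 14.3% for one undosed subject and 25.0% for two.

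With exactly 8 enrolled:

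| Undosed | Subjects with a TEAE | Among dosed | As written |
|---|---|---|---|
| 1 | 2 | 2/7 = 28.6% | 2/8 = 25.0% |
| 1 | all 7 dosed | 7/7 = 100% | 7/8 = 87.5% |
| 2 | 2 | 2/6 = 33.3% | 2/8 = 25.0% |
| 2 | all 6 dosed | 6/6 = 100% | 6/8 = 75.0% |

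**How likely is it?**

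The documents give no rate. If each of 8 enrolled subjects independently had an assumed chance q of going undosed, the chance of at least one is 1 − (1 − q)^8. This is 7.7% for q = 1%, 33.7% for q = 5% and 57.0% for q = 10%.

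**The case against.** The strongest reply is that the problem may never arise. The sample-size text treats enrolment and dosing as going together. There is one open-label treatment without randomisation, with admission on Day -1 and dosing on Day 1, so the interval looks short. This stands as a limit on likelihood. It does not change the definition, because Protocol 8.1.1 treats the two as separate events.

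A second reply is that SAP 8 lets protocol deviations be weighed when subjects are assigned to populations. An ineligible subject could be removed that way. This is partial mitigation: it is discretionary, gives no rule for undosed subjects, and need not reach someone who withdraws before dosing without any deviation.

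Third, the denominator is inferred from SAP 9.1, which says only that the restriction generally applies, and the table shells are a separate document not available here. They might divide by the number dosed. If so, they would depart from the SAP's own definition, and the sentence would still need correcting.

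Fourth, little else is affected. The number of AEs, the number of affected subjects and all listings stay the same. Laboratory data are listed only, ECGs are not presented, and an undosed subject has no postdose vital signs. The PK population requires a dose, and no safety inference is planned (SAP 9.4.8). All of this stands and keeps the point modest.

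A reader might infer that undosed subjects have no data at all. The documents do not support that. Protocol 8.1.1 stops only further collection, screening data would exist, and Protocol 9.2.1 confirms recording from consent: "Although all AEs are recorded in the eCRF after signing informed consent". What is missing is postdose data.

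**Conclusion.** The point holds as a conditional one. The stated rule gives too low a TEAE percentage whenever an enrolled subject is not dosed. The relative understatement is U/(D+U): 11.1% to 14.3% for one such subject with 8 to 6 dosed, and 20.0% to 25.0% for two. These figures rest on assumed values of U and on reading SAP 9.1 as setting the denominator.

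Two stronger readings might tempt a reader. One is that the percentages are in fact diluted; nothing in the documents shows that any subject went undosed, and with none the effect is zero. The other is that the SAP and protocol conflict; they agree, and the gap is common to both. The primary bioavailability analysis is untouched. The correction is still worth making, because the endpoint is a named one, the sample is small, and the denominator should not be left to judgement in an open-label study.

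**What to change.** In SAP 8, replace the definition with wording such as: Safety population: every enrolled subject who received any amount of oral LY3314814 or of IV [13C4 15N3]-LY3314814, regardless of completion of the protocol. In SAP 9.4.1, name this population as the denominator for TEAE percentages. Show subjects enrolled but not dosed in disposition and listings only, so that any AE recorded between consent and withdrawal remains visible.

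Record the departure from Protocol 10.3 in SAP 11, which now reports no changes. SAP 3 says the SAP supersedes the protocol's statistical considerations, so a protocol amendment is not required. Protocol 10.3 can be aligned if the protocol is amended for another reason.

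The cost is one replaced sentence, one added denominator statement, an entry in SAP 11, and a check that the table shells agree. No data collection, sample size or PK analysis changes.
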